Study Title: Coupler-Based Hearing-Aid Fitting Approach for Experienced Users

NCT02772757

ID: C1895-P

Principal Investigator: [name], Au.D., Ph.D.

April 30, 2015

The purpose of this study is to evaluate procedures designed to greatly improve the efficiency of hearing-aid delivery to experienced hearing-aid wearers. Specifically, the fitting accuracy and patient experience for two approaches that would not require additional direct patient contact will be compared to the current standard-of-care (SoC) approach in which *in situ* real-ear aided responses (REARs) measures are obtained. The proposed approaches use derived REAR hearing-aid fittings based on either (1) average-corrected or (2) individually-measured real-ear to coupler differences (RECDs) for fitting and verification of *replacement* amplification. The primary research aims are to determine:

- 1. if the *in situ* REARs differ from the derived REARs in the experimental groups and if the derived REARs in the experimental groups differ from the *in situ* REARs in the SoC group,
- 2. if fittings based on measured versus average-corrected RECD values differ in the experimental groups, and
- 3. if the subjective hearing-aid outcomes differ among the groups.

RESEARCH DESIGN AND METHODS

Design. A mixed model, repeated measure design will be used in the current study.

Participants. There will be three groups of participants. One group will serve as the active-control group and will receive the standard-of care 30-min appointment (SoC group). One experimental group will have the average-corrected (for venting) RECD (Exp-AVGc Group) incorporated during the RECD-based verification and the other experimental group will have the measured (with custom earmold) RECD (Exp-M Group) incorporated during verification. The two experimental groups will be mailed their replacement hearing aids *after* they are programmed and verified with RECD-based fittings. The participants will be randomly assigned to each group.

Inclusion Criteria: Participants will be included in the study if the following criteria are met:

- experienced BTE hearing-aid users who are obtaining replacement VA-issued BTE hearing aids coupled to a custom earmold that is simply an upgrade in model (e.g., 2010 Phonak Exeila 211 Art BTE upgrading to a 2014 Phonak Bolero Q90 BTE) with the same style earmold
- no more than a moderate sensorineural hearing loss (defined as < 60 dB HL pure-tone average at 500, 1000, and 2000 Hz AU)
- ability to read and write in English as determined by reading a few sentences from the consent document aloud so that self-report measures can be completed

Exclusion Criteria: Participants will be excluded if any of the following criteria are true:

- outer or middle ear pathology as determined by otoscopy, immittance, and/or audiometric testing (e.g., conductive or mixed losses)
- lack of phone or non-use of the phone as the participants will be required to conduct a telephone interview after they obtain their replacement hearing aids
- unwilling or unable to be mailed hearing aids
- co-morbid condition that would preclude their participation as determined by a chart review (e.g., dementia, visual impairment/legal blindeness, substance abuse, etc.)

Materials/Tests:

In addition to RECD and REAR measures, this study will include measures of speech-in-noise abilities and hearing-aid outcomes. These measures are described below:

Client-Oriented Scale of Improvement (COSI; Dillon, James, & Ginis, 1997). The listener nominates up to five listening goals on the COSI. After hearing-aid use, the listener assesses two outcomes for each goal. One outcome is the "degree of change" relative to the patient's unaided experience. Responses are recorded on a categorical scale from 'worse' to 'much better.' The second outcome is the final satisfactory "aided" ability for each goal as measured on a categorical scale from hardy ever (10%) to almost always (95%). The percentage of 'better' and 'much better' responses and the average of the final ability will be calculated across goals. (Session 1—goals established and Session 3—outcomes established—See Procedure Section below) (5 minutes). Device Oriented Subjective Outcome (DOSO) Scale (Cox, Alexander, & Xu, 2009). The questionnaire is comprised of 28 items making up the following six subscales related to listening performance with hearing aids: (1) speech cues, (2) listening effort, (3) pleasantness,(4) quietness, (5) convenience, and (6) use. Responses from 'not at all' (1 point) to tremendously (7 points) are recorded for each item. Higher scores represent better device-oriented subjective outcome. This is a post-only measure (Session 3) (10 minutes).

Satisfaction with Amplification in Daily Life (SADL) (Cox and Alexander, 1999). The SADL questionnaire has 15 items that examine self-reported hearing-aid satisfaction. The following four subscales are included: (1) positive effect, (2) negative features, (3) personal image, and (4) service and cost. For the current study, item 14 on the service and cost subscale was not used as the Veterans were not charged for the cost of their bilateral hearing aids. The SADL uses a 7-item response scale in 1-unit steps, 1 (poorest) to 7 (highest) for each item, which are averaged for each subscale and total scale score. (Session 3) (5 minutes).

Words-In-Noise (WIN) test uses the NU-6 materials in a six-talker multi-talker babble. The words are presented at 7 signal-to-noise ratios (S/N), 24-dB to 0-dB S/N, in 4-dB decrements. The noise level remains constant and the level of the words varies. Listeners with pure-tone averages ≤25-dB HL will be presented with noise levels at 70-dB SPL and the words will vary from 94- to 70-dB SPL. Listeners with pure-tone averages 25.1- to 40-dB HL will be presented with noise levels at 80-dB SPL and the words will vary from 104- to 80-dB SPL. Listeners with pure-tone averages between 40.1- and 60-dB HL will be presented with noise levels at 90-dB SPL and the words will vary from 114- to 90-dB SPL (following Wilson, 2003; Wilson, Abrams, & Pillon, 2003; Wilson & Burks, 2005). The 50% point on the WIN will be calculated for each ear using the Spearman-Kärber equation (Finney, 1952) in addition to the percent correct performance at each signal-to-noise ratio. (Session 1) (5 minutes).

Procedures.

Session 1 (Baseline, Pre-Fitting). All testing will be completed separately in each ear for all groups. Otoscopy will be performed and cerumen management completed as needed. The standard audiometric evaluation including air- and bone-conduction pure-tone audiometry; word-recognition in quiet (NU-6 words) and in noise (WIN) will be completed. Tympanometry and aural acoustic reflexes also will be measured. The COSI will be completed to obtain the listening goals of the participant and to facilitate programming needs of the replacement hearing aids (e.g., whether or not manual programs are needed/desired). In addition, an intake form (**Appendix 2**) will be completed for all groups to determine other device options and function (e.g., volume control options such as yes/no or unlinked/linked; removal filament or not; earmold style from previous order form; and tubing length; etc.). If care or use questions arise based on responses on the intake form, then they will be answered during this session. The replacement hearing aids and earmolds will be ordered using the earmold scans on file with the manufacturer provided that the current earmolds from the old hearing aid are a good fit. If not, then ear impressions will be made for replacement earmolds.

For the experimental groups, the tubing length of the current earmolds will be measured carefully so that the replacement earmold tubing can be cut to the same length at the RECD-fitting (Session 2-below). For the Exp-AVGc group, the current earmold vent size will be measured if the actual size is not available on the previous order form. That way, the average RECD values can be corrected for the vent size of the earmold at the RECD-fitting (Session 2).

For the Exp-M group only, RECD values will be obtained separately for each ear with the patient's current earmolds after they have been cleaned and tubing changed as needed. Using the current earmold as opposed to the foam insert will allow venting and tubing characteristics to be incorporated in the RECD-fitting. The RECD measurement protocol will follow the standard clinical protocol and will use the Verifit 2 system. The test box reference microphone will be calibrated. The RECD transducer will be placed on the BTE coupler and the coupler response will be obtained. The probe tube will be inserted 25-27 mm from the antitragal notch in order to ensure placement

within approximately 2-5 mm from the eardrum. The participant's current earmold (lubricated to ensure a good seal) will be placed in the ear canal and care will be taken not move the probe tube during earmold insertion. The RECD transducer will be coupled to the earmold tubing and the realear response will be obtained. The difference between the coupler and real-ear responses is the measured RECD.

Session 2: The Intervention 'Visit'.

Soc Group Fitting. This group will receive the SoC, 30-minute face-to-face fitting appointment 4-6 weeks after Session 1, the average wait time for a fitting appointment. The right and left hearing aids will be programmed separately to the National Acoustics Laboratory Non-Linear 2 (NAL-NL2) prescription. The REAR of the hearing aids will be verified to the 50-, 65-, and 75-dB SPL prescriptive targets generated by the Verfit 2 system using the speechmap stimulus. The criterion for an appropriate fitting would be ± 3 dB between the output and the prescriptive target from 250 Hz to the frequency in which the unaided threshold crossed the 65-dB SPL target. The Real Ear Saturation Response (RESR) will be measured using an 85-dB swept pure-tone to ensure that the maximum output of the hearing aids does not exceed the predicted uncomfortable loudness levels of the participant. The programming options will be optimized based on the information obtained on the intake form (**Appendix 2**). The participant will be provided with the manufacturer brochure, programming report from the manufacturer software, and the VA Hearing Aid Booklet. Consistent with current SoC, no orientation will be provided.

Experimental Group Fittings. The participants in the experimental groups will not be present during the fitting. The hearing aids will be fitted in a manner similar to the SoC fitting except the average-corrected (for vent size) RECD (Exp-AVGc Group) or measured RECD from Session 1 (Exp-M group) will be inputted into the Verfit 2 to generate the prescriptive targets and the derived REARs will be obtained following the standard clinical procedure. In short, the tubing of the *replacement* earmold will be cut to length and coupled to each hearing aid. The earmold will be attached to the HA-1 coupler with putty ensuring that the eartip is flush against the opening of coupler and the vent sealed, as is standard with this procedure. The hearing aids will be programmed and the derived REARs will be obtained and verified against the prescription. After programming and verification, the hearing aids will be mailed to the patient along with the manufacturer brochure, programming report from the manufacturer software, and the VA Hearing Aid Booklet within one business day of their receipt from the manufacturer. It is estimated that these experimental fittings will take 15 minutes, or half the time of the SoC fittings. A signature will be required to accept the delivery and the delivery will be tracked.

Two-Day Follow-Up Phone Call. All participants will receive a 2-day follow-up phone call after the hearing-aid fitting. The experimental groups will be phoned after delivery of the hearing aid is confirmed with the delivery receipt. A telephone script (**Appendix 2**) will be used to ask questions about the physical comfort of the device, sound quality, and any other hearing-aid problems or questions.

Session 3 (One-Month Post-Fitting). One month after the hearing-aid fitting, all groups will return to complete subjective outcome measures. The measures will be presented in random order. The COSI outcomes will be measured to determine if the hearing aids are meeting the patient-nominated goals. The SADL will be completed and the *Service and Cost* subscale will be of great interest due to the service-related items that may differentiate between groups. The DOSO will be used as it assesses hearing-aid outcomes in six domains. An exit survey (**Appendix 2**) also will be administered to gain insight into the perceptions related to service delivery, access, and convenience. In addition, *in situ* REARs will be obtained from all groups using the current programming from the replacement aids. These *in situ* REARs will allow within and between group comparisons regarding the hearing-aid function and determine the accuracy of the experimental fittings relative to the SoC fittings. The repeat *in situ* REAR measurements in the SoC group (i.e., Sessions 2 and 3) will serve to assess the inherent variability with *in situ* REAR measurements and

will facilitate interpretation of REAR data when comparing the accuracy of the *in situ* and derived REARs in the experimental groups.

Attrition. In our experience ([name] and [name]) with a multi-session (4 sessions over 6 months), hearing-aid clinical trial, we had a low local attrition rate of 8.7%. The primary reasons for withdrawal were due to personal reasons which included illness, moving out of state, and transportation issues during inclement weather (i.e., snow). Thus, we considered a conservative estimate of 15% attrition for the proposed multi-session study.

Sample Size. Based on an expectation that REAR measurements should be within 2 dB on average across frequency, and an SD of 2, then 18 participants are needed for each group (total N = 54) assuming a power of at least β = .80 and *p* = .05. Considering 15% attrition, then 9 additional subjects will be needed (N = 63) resulting in 21 participants per group. Participants will be recruited from the Mountain Home VA audiology clinics. Last year, our clinic served 7,481 Veterans during 16,278 patient visits and dispensed 7,134 hearing aids. Also, based on the national average, it is estimated that ~50% of VA hearing aids dispensed are replacement hearing aids for experienced users. Thus, we anticipate no difficulty in recruiting the target sample at Mountain Home.

Data Analysis.

Specific Aim 1 and 2. A mixed-model analysis of variance (ANOVA) will be conducted. This analysis will examine differences (in dB SPL) for REAR (actual vs derived using average vs measured RECD) across frequency and ears within and between the groups. This analysis will determine (1) if the *in situ* REARs differ from the derived REARs in the experimental groups and if the derived REARs in the experimental groups differ from the *in situ* REARs in the SoC group (2) if coupler-derived REARs using average-corrected or measured RECDs differ; and (3) if the average-corrected RECD.

Specific Aim 3. A multivariate ANOVA will be conducted to examine group differences among the outcome measure subscales. A logistic regression also will be conducted to examine if the proportion of responses differ among the groups on the specific telephone and exit survey items of interest.

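### The COSI change item is anchored to unaided listening in experienced users and may be insensitive to fitting method; a Session 1 rating with the current aids is a cheap improvement

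*Combined protocol and SAP*

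**What the plan says.** Inclusion Criteria limits entry to "experienced BTE hearing-aid users who are obtaining replacement VA-issued BTE hearing aids coupled to a custom earmold that is simply an upgrade in model".

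The COSI entry under Materials/Tests says: "The listener nominates up to five listening goals on the COSI". Each goal then receives two outcomes. Degree of change is judged "relative to the patient's unaided experience" on a categorical scale running from worse to much better. Final aided ability is a categorical rating from 10% to 95% with no reference state. On scoring: "The percentage of 'better' and 'much better' responses and the average of the final ability will be calculated across goals".

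At Session 1 the COSI is used only to set goals and guide programming. Both COSI outcomes are collected at Session 3. DOSO is described as post-only, and SADL is also given at Session 3. Data Analysis, Specific Aim 3, compares the groups on the outcome subscales by multivariate ANOVA. The sample size rests on REAR and does not consider any subjective measure.

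**The concern.** Aim 3 asks whether subjective outcomes differ among three ways of fitting a replacement aid. All three arms receive aids programmed and verified to a prescription. Against an unaided reference, part of every participant's change score is the benefit of wearing an aid at all, which does not depend on arm. Established users must also recall a state that they may have left some time ago.

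Pooling the top two categories adds to the problem. A modest loss from a mailed fitting could move answers from *much better* to *better*, and the percentage would not register that move.

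At stake is how a null result is read. Similar high percentages in all arms could be taken as support for mailed fittings when the item had only a modest chance of showing a loss. A further gap is that no COSI rating is taken with the current aids, so even the unanchored final-ability outcome has no baseline to adjust for.

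**Working it through.** **1. The plan's own figure.** Sample Size gives a 2 dB difference, SD 2, power 0.80 and p = .05 (taken as two-sided). Then n per group = 2(1.96 + 0.84)²(2/2)² = 15.7, so 16, or 17 with the t distribution. The stated 18 is consistent with this. With 21 enrolled and 15% lost, 21 × 0.85 = 17.9 remain, so 18 per arm is used below. This figure concerns REAR and does not bear on COSI.

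**2. Sensitivity of the pooled percentage.** The documents give no COSI rates, so everything here except n and the maximum of five goals is assumed. Each goal rating is a mean m plus a person effect (SD 0.7) plus a goal effect (SD 0.7). The total SD is √(0.49 + 0.49) = 0.99 and the within-person correlation is 0.5. A goal counts as favourable when its rating exceeds 0, so the expected share is Φ(m/0.99). The mailed arm has m lower by 0.7. Each person's share over five goals is compared between two arms of 18 by a two-sided t-test at 0.05, with power by simulation.

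| m in SoC | SoC favourable | Mailed favourable | Power |
|---|---|---|---|
| 2.5 | 99.4% | 96.5% | 0.09 |
| 2.0 | 97.8% | 90.5% | 0.32 |
| 1.5 | 93.5% | 79.0% | 0.50 |
| 1.27 | 90.0% | 71.8% | 0.57 |
| 1.0 | 84.4% | 61.9% | 0.62 |
| 0.5 | 69.3% | 42.0% | 0.67 |
| 0.0 | 50.0% | 24.0% | 0.66 |

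A second set of assumptions (true difference 0.5 SD of the goal rating) gives the same pattern. With within-person correlation 0.3, an uncapped rating has power 0.59, and the pooled percentage has 0.47, 0.39, 0.31 and 0.18 when the better arm is at 80%, 90%, 95% and 98%. With correlation 0.5 the figures are 0.47 uncapped and 0.38, 0.32, 0.24 and 0.14.

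**3. Re-anchoring the change item to the old aids.** In the step 2 model, moving SoC from 98% to 50–70% favourable appears to lift power from 0.32 to about 0.67. That holds the between-person SD at 0.7. A change score against the old aid also carries variation in how good that aid was. Adding a person-level SD of 0.5, 0.7 or 1.0 (assumed) lowers power at 50–70% to about 0.53, 0.43 or 0.31.

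**4. Adding a Session 1 rating as a covariate.** Using the step 2 variances and an uncapped rating averaged over five goals:
- variance of a person's mean = 0.49 + 0.49/5 = 0.588, so SD = 0.767;
- standardised loss d = 0.7/0.767 = 0.913;
- noncentrality = 0.913 × √(18/2) = 2.74, giving power of about 0.76 (about 0.75 by simulation).

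Adjusting for a baseline with correlation r replaces d by d/√(1 − r²):
- r = 0.3: d = 0.957, power 0.80;
- r = 0.5: d = 1.054, power 0.87 by formula, about 0.85 by simulation of the fitted model;
- r = 0.7: d = 1.278, power 0.96.

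All powers are for one pair of arms, without a multiplicity adjustment.

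**The case against.** A reader might infer that the item sits at ceiling and cannot separate the arms. The documents do not support either statement. They give no COSI distribution. Goals are nominated by people already wearing aids, so they may be residual difficulties on which favourable answers fall well short of 100%. Sensitivity declines without vanishing: about 0.50 at 94% favourable and 0.32 at 98%, with a severe loss only near 98% or above. It is also not stated that the aids being replaced are in good working order.

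A reader might also infer bias. Participants are randomised and the reference is the same in every arm, so it costs sensitivity without by itself distorting the contrast.

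Aim 3 does not depend on this item. COSI final ability, six DOSO subscales and four SADL subscales carry no unaided anchor, and Session 3 singles out the SADL service and cost subscale as of special interest. COSI change is not named as primary. The exit survey and telephone script are in Appendix 2, which is not shown, so a question comparing old and new aids may exist there.

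These points stand and limit the severity. They do not remove the mismatch between reference state and population, the information lost by pooling, or the absence of a pre-fitting value on the scales described.

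**Conclusion.** The concern holds as a cheap improvement of low to moderate severity. The unaided anchor and the pooled scoring are in the text, and together they risk a ceiling and low sensitivity to fitting method. How large the loss is depends on a favourable-answer rate that the documents do not give: small at 80% or below, material at 95%, serious at 98%.

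The firmer gain comes from the missing baseline. For a loss of 0.7 latent SD with 18 per arm, adjustment raises power for final ability from about 0.75 to between about 0.80 and 0.96 over baseline correlations of 0.3 to 0.7. These figures assume five goals per person and a continuous, uncapped rating. The real 10% to 95% categories, and participants with fewer goals, would lower the absolute values. Rewording the change item is less secure, because variation among old aids can cancel the benefit.

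**What to change.** At Session 1, when goals are nominated, have each participant also rate the COSI final-ability item (10% to 95%) for each goal with the current aids. Take the rating before the group-specific steps of that session, so that knowledge of allocation cannot affect it. Add one line to Specific Aim 3: compare groups on Session 3 mean final ability, adjusted for the Session 1 mean over the same goals. State that the unaided-reference percentage of *better* and *much better* is descriptive.

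The cost is one to two extra minutes on a form already being completed. The rating has to be taken before the replacement fitting, because it cannot be recovered cleanly afterwards.

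Rewording degree of change to refer to the previous aids is optional. It would give up comparability with unaided-reference COSI scores, for a gain that old-aid variation may offset.

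### The Aim 3 subscale analysis names no baseline covariate although the Session 1 WIN score is available in all groups: an optional gain in precision, not a bias

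*Combined protocol and SAP*

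**What the plan says.** **Baseline data.** Under Procedures, Session 1, "The standard audiometric evaluation including air- and bone-conduction pure-tone audiometry; word-recognition in quiet (NU-6 words) and in noise (WIN) will be completed", and "All testing will be completed separately in each ear for all groups". The Materials/Tests entry for the WIN adds that "The 50% point on the WIN will be calculated for each ear".

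**Outcomes.** No questionnaire outcome is scored before fitting. Of the DOSO the plan says "This is a post-only measure (Session 3". The SADL items are rated 1 to 7, "which are averaged for each subscale and total scale score. (Session 3) (5 minutes". For the COSI, goals are set at Session 1 and outcomes are scored at Session 3.

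**Analysis.** Under Data Analysis, Specific Aim 3: "A multivariate ANOVA will be conducted to examine group differences among the outcome measure subscales". For the telephone and exit survey items, "A logistic regression also will be conducted to examine if the proportion of responses differ among the groups". Neither sentence names a covariate, and the Data Analysis section gives the WIN no role. Assignment to groups is random. The method is not described and no stratification is mentioned.

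**The concern.** Without a pre-fitting score for an outcome, the next best source of precision is a baseline variable that predicts it. The trial has a candidate in every participant and does not plan to use it.

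A link is plausible from the protocol's own content. The DOSO covers speech cues and listening effort, and the COSI scores final aided ability on listening goals. Hearing ability is also likely to vary: eligibility requires a pure-tone average below 60 dB HL with no stated floor, and WIN presentation levels are set for three pure-tone bands.

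At stake is the sharpness of Aim 3, one of the three primary research aims. The sample size rests on REAR in dB, and no SD or target difference is given for any questionnaire. Aim 3 therefore has no demonstrated power.

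**Working it through.** **Inputs from the documents.** Target of 18 per group (54 in all); 21 per group enrolled (63) to allow for 15% attrition; alpha 0.05, taken as two-sided because sidedness is not stated.

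**Assumptions, not in the documents.** A questionnaire difference of d = 0.8 SD, for illustration, and a WIN–outcome correlation r, shown from 0 to 0.5.

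**1. The plan's own figure.** A 2 dB difference with SD 2 gives d = 1.0. A two-sample t-test at 80% power needs 16.7, so 17 per group. At 18 per group power is 0.83. The stated 18 is sound for REAR, and nothing below depends on an error in it.

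**2. Chance imbalance.** The SE of a standardised baseline difference between two groups of 18 is √(2/18) = 0.333.
- P(|difference| ≥ 0.5 SD) = P(|Z| ≥ 0.5/0.333) = P(|Z| ≥ 1.5) = 0.134.
- With 21 per group the SE is √(2/21) = 0.309 and the probability is 0.105.
- A gap of 0.5 SD shifts an unadjusted contrast by 0.5 × r, which is 0.15 SD at r = 0.3 and 0.25 SD at r = 0.5.

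**3. Unadjusted pairwise power.** Noncentrality 0.8/0.333 = 2.40 on 34 df gives power 0.645.

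**4. Power with one covariate, its cost charged.** The residual SD is √(1 − r²). Error df fall from 34 to 33. Expected covariate imbalance inflates the variance of the contrast by 1 + 1/32 = 1.031. Noncentrality is therefore 0.8 / [0.333 × √(1 − r²) × √1.031].

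| r | Residual SD | Noncentrality | Power |
|---|---|---|---|
| 0 | 1.000 | 2.36 | 0.63 |
| 0.2 | 0.980 | 2.41 | 0.65 |
| 0.3 | 0.954 | 2.48 | 0.67 |
| 0.4 | 0.917 | 2.58 | 0.71 |
| 0.5 | 0.866 | 2.73 | 0.755 |

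Against 0.645, the change is a loss of about 0.01 at r = 0, nil at r = 0.2, and a gain of about 0.03, 0.06 and 0.11 at r = 0.3, 0.4 and 0.5.

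**5. One covariate or two.** Suppose the pure-tone average is added and the pair explains no more than one covariate would (joint R² = 0.09, 0.16, 0.25). Error df are then 32, the inflation is 1 + 2/31 = 1.065, and power is about 0.66, 0.69 and 0.74. A second covariate pays only if it explains variance that the WIN does not.

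These are two-group calculations and serve as a guide. In the three-group model one covariate takes error df from 54 − 3 = 51 to 50, a smaller cost.

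**The case against.** The strongest reply is that nothing in the plan is wrong. With random assignment an unadjusted MANOVA is valid, and collecting a baseline measure creates no duty to adjust for it. Audiometry already serves eligibility, the WIN presentation level and the fitting criterion. The plan is silent on covariates rather than committed to omitting them. All of this stands, and it is why the point is a refinement.

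Two further objections also stand. The benefit depends wholly on an unknown r and vanishes at about 0.2. The link is also selective: the documents give no reason why speech-in-noise ability should predict satisfaction with service delivery, yet the Session 3 text singles out the SADL service and cost subscale as of great interest. Little gain should be expected there, or for personal image.

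A reader might infer more than the documents support:
- **That the Aim 3 comparisons are biased or confounded by hearing ability.** Random assignment rules that out in expectation.
- **That simple randomisation makes imbalance common.** The method is not stated, and about 13% for one given pair is not common.
- **That the COSI has no reference point at all.** Its degree-of-change rating is made against the unaided experience, which is recalled rather than measured.

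The objection does not remove the core of the point. The covariate is already collected in all groups, no outcome has a measured baseline, and the worst-case cost of adjusting is about 0.01 in power.

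**Conclusion.** The point holds as a minor, optional improvement. The planned comparison is unbiased. It forgoes some precision and leaves chance imbalance uncorrected, chiefly for DOSO speech cues and listening effort and for COSI final ability, if that score is among those analysed (the plan does not list them). At 18 per group and d = 0.8, the change in power runs from a loss of about 0.01 (r = 0) to a gain of about 0.11 (r = 0.5). This rests on assumed values of r and d and on a pairwise comparison standing in for the three-group test.

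**What to change.** Add to Specific Aim 3 that the subscale models include one pre-specified covariate, the Session 1 WIN 50% point averaged over the two ears, as a MANCOVA or as an ANCOVA for each subscale. Report the unadjusted MANOVA as a sensitivity analysis. Leave the logistic regressions for the telephone and exit survey items unadjusted, because a covariate there changes the meaning of the odds ratio. Naming the covariate in advance also prevents its choice after the results are seen.

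The cost is a sentence or two in the plan, one error degree of freedom, and about 0.01 power if r is near 0. No new data or visits are needed.

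### Does measuring the Exp-M RECD through a current earmold that is about to be remade for poor fit undermine the Aim 1 comparison?

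*Combined protocol and SAP*

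**What the plan says.** All of this is in the combined protocol and SAP.

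- **Inclusion Criteria.** Entry is limited to experienced users receiving a model upgrade "with the same style earmold". This fixes the style, not the fit.
- **Procedures, Session 1, default mold source.** "The replacement hearing aids and earmolds will be ordered using the earmold scans on file with the manufacturer provided that the current earmolds" fit well.
- **Session 1, exception.** "If not, then ear impressions will be made for replacement earmolds". Nothing is added about the RECD in those ears.
- **Session 1, Exp-M RECD.** Each ear is measured through the current mold after cleaning and any re-tubing. The reason given is: "Using the current earmold as opposed to the foam insert will allow venting and tubing characteristics to be incorporated in the RECD-fitting". The one safeguard described for the seal is that the "current earmold (lubricated to ensure a good seal) will be placed in the ear canal".
- **Session 2, Experimental Group Fittings.** The "RECD from Session 1 (Exp-M group) will be inputted into the Verfit 2 to generate the prescriptive targets", with the participant absent. No re-measurement with the replacement mold is described.
- **Session 3.** In situ REARs are taken with the replacement aids in all groups. The repeat measurements in the "SoC group (i.e., Sessions 2 and 3) will serve to assess the inherent variability" of in situ REARs.
- **Data Analysis, Specific Aim 1 and 2.** A mixed-model ANOVA over REAR type, frequency, ear and group asks, among other things, whether in situ "REARs differ from the derived REARs in the experimental groups". Earmold source is not a term in the model.

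**The concern.** The case for using the current mold is that it carries its venting and tubing into the fitting. That case is weakest where the mold is being remade because it does not fit. In such an Exp-M ear the derived REAR rests on the old mold and the in situ REAR on the new one, so their difference mixes two errors: that of the measured-RECD method and that of the changed mold. One concerns the method; the other concerns which patients suit it.

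The repeat SoC measurements cannot separate the two, because no RECD from an old mold enters the SoC fitting. If Exp-M showed a difference and nobody knew which ears had new impressions, the result could not be re-examined in the ears least likely to be mismatched.

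**Working it through.** **The plan's own figure.** Sample Size gives a 2 dB difference, SD 2 dB, power 0.80 and alpha 0.05, leading to 18 per group. A two-sided two-sample t-test with standardised difference 2/2 = 1 needs 16.7, so 17 per group; at 18 the power is 0.83. The stated 18 is consistent with power of at least 0.80. A paired t-test with n = 18 and SD of differences 2 dB has power 0.98 for 2 dB.

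**Assumed inputs.** The documents give none of these.

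- q, share of Exp-M participants affected: 0.20 (range 0.10 to 0.40; of 18, about 2 to 7).
- s, RECD error at affected frequencies: 5 dB (3 to 10).
- f, fraction of frequencies affected: 1/2 (1/3 to 1/2).
- SD of paired differences without mold error: the planning value of 2 dB.

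**Formulas.** The participant-level error is e = f × s if both ears are affected, and half that if one is. If all errors have the same sign, the mean shift is q × e and the SD is √(4 + q(1 − q)e²). The rejection rate is that of a two-sided paired t-test with n = 18 when ears with an unchanged mold have no true difference.

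| Case | e (dB) | Shift (dB) | SD (dB) | Rejection rate |
|---|---|---|---|---|
| Low (0.10, 3, 1/3), one ear | 0.5 | 0.05 | 2.01 | 0.051 |
| Low, both ears | 1.0 | 0.10 | 2.02 | 0.055 |
| Central (0.20, 5, 1/2), one ear | 1.25 | 0.25 | 2.06 | 0.077 |
| Central, both ears | 2.5 | 0.50 | 2.24 | 0.146 |
| High (0.40, 10, 1/2), one ear | 2.5 | 1.00 | 2.35 | 0.400 |
| High, both ears | 5.0 | 2.00 | 3.16 | 0.715 |

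Central, both ears: e = 0.5 × 5 = 2.5; shift = 0.2 × 2.5 = 0.5; SD = √(4 + 0.2 × 0.8 × 6.25) = √5 = 2.24.

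If the errors have mixed signs, the mean does not move and the SD is √(4 + q·e²). Central, both ears: √(4 + 0.2 × 6.25) = 2.29, and paired power for 2 dB is 0.94 instead of 0.98. At the low end it stays at 0.98; at the high end it is 0.57.

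**Which contrasts are touched.**

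1. *In situ versus derived within Exp-M (Aim 1).* The error appears here. The aim is whether the two differ, and the stated purpose is to evaluate delivery procedures, including fitting accuracy. A shift from a remade mold is part of that accuracy, so the rejection rates above are not false-positive rates for the question the plan poses. They would be so only for a narrower question: method error with an unchanged mold.
2. *Exp-M derived REAR versus SoC in situ REAR, and measured versus average-corrected RECD.* Both use a derived REAR that is programmed and verified against the prescription at Session 2. A mold mismatch appears mainly later, in situ, so these contrasts are touched far less directly.
3. *Between-group comparison of Session 3 in situ REARs.* Added Exp-M variance matters here. With mixed signs and both ears affected, two-sample power for 2 dB falls from 0.83 to 0.77 in the central case (2/√((4 + 5.25)/2) = 0.93 standardised) and to 0.49 at the high end. The low end leaves it at 0.83.

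**What a restricted analysis would offer.** Dropping 10%, 20% or 40% of participants leaves about 16, 14 or 11 per group. Paired power for 2 dB becomes 0.96, 0.93 or 0.85, and two-sample power 0.78, 0.72 or 0.61. Every ear receives a new mold, so some mold-change error would remain in the retained ears.

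**The case for a change.** The strongest argument for a change is cost. One field per ear (scan on file or new impression), counts by group and one sensitivity analysis would leave N = 63 and the primary analysis untouched, and an exclusion chosen in advance is more credible than one chosen after the data are seen. The likely rebuttals do not dispose of the gap: lubrication helps the seal but does not make a poorly fitting mold match a newly impressed one, and the same-style requirement says nothing about fit.

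Much of this stands. The gap is real, and a record of mold source would help interpretation if Exp-M showed a difference. It falls short of requiring a change for three reasons.

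- The source may be recoverable without a new rule. Taking an impression or ordering from a scan is an ordering event, Session 1 already refers to earmold order forms, and the intake form in Appendix 2 (not in the supplied text) may record it.
- The restricted analysis would rarely settle the cause. It removes few participants, loses precision and leaves some of the error in place.
- Carry-over from the old mold is not peculiar to Exp-M. Exp-AVGc may also take its vent size from the current mold, so the restriction would not cleanly isolate the measured-RECD method.

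**Conclusion.** The plan does measure every Exp-M RECD through the current earmold, including ears sent for a new impression, and the visible text sets out no flag or analysis for them. The provisions do not contradict each other. The all-ears comparison validly answers the question asked, because it describes the pathway participants receive. The issue is attribution of cause, not type I error, and a careful analyst can deal with it in interpretation.

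Its size is unknown. With 20% of Exp-M participants affected and 5 dB at half the frequencies, the mean shifts by 0.25 dB (one ear) to 0.5 dB (both ears). At the low end it is 0.05 to 0.10 dB, which is negligible. The full planning difference of 2 dB is reached only if the share, the error and both-ear involvement are all extreme and the errors share one sign. The subgroup is probably small, because entry requires the same style of mold and the scan on file is the default.

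These figures rest on assumed inputs and on a paired t-test of a frequency average, a simplification of the planned mixed-model ANOVA. On that footing, neither N, the primary analysis nor the procedure needs to change.
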